- ^v Every 13-week in-clinic visits are no longer required and may be changed to every 26-week in-clinic visits (at the option of the investigator). Accordingly, study drug may be supplied every 13 or 26 weeks. If in-clinic visits are changed to a every 26 week frequency, a telephone contact should occur in between the 26-week in-clinic visits such that there will be a contact with the subject every 13 weeks (in-clinic visit alternating with telephone contacts). At each telephone contact, investigators should ask subjects about any foot problems and remind them about routine preventative foot care and early intervention for foot problems.

POSTTREATMENT TIME AND EVENTS SCHEDULE – SUBJECTS WHO PREMATURELY DISCONTINUE STUDY MEDICATION

Phase	Double-Blind Visit Schedule (Posttreatment)										
	- Starting at the nearest post-randomization week after the Follow-up					Contact Visit -					
Procedures and Evaluations											
Week ^a	2, 4 (TC) ^b	6	(TC) ^b	9	12	18	26	39	52	78 to end ^e	104 to end ^e
Procedures											
Vital signs, weight, Foot examination ^c		X		X	X	X	X	X	X	X	X
Provide container for urine collection for first morning void		X						X		X (foot examination only)	X
Serum creatinine		X			X	X	X	X	X		X
HbA _{1c}			X	X	X	X	X	X	X		X
Fasting serum lipids				X	X	X	X	X	X		X
First morning void urine for albumin/creatinine ratio ^d				X	X	X	X	X	X		X
Ongoing review											
Serious adverse events and adverse events of fracture	X	X	X	X	X	X	X	X	X	X	X
AHA agents after study drug discontinuation											At final visit or contact
Events in CV composite endpoint	X	X	X	X	X	X	X	X	X	X	X

^a After Week 78, on those occasions when the 26- and/or 52-week-interval visits overlap each other, the visit with the more comprehensive procedures will be followed.

^b Telephone contact (or an optional, unscheduled site visit, at the discretion of the investigator) will be made at Weeks 2, 4, and 9 to check the subject's status, including discussing the subject's diary entries and any CV events or adverse events. If a telephone contact or study visit is not possible, follow-up information may be collected via email or other electronic or non-electronic means.

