Figure 2 shows the intended follow-up of randomized subjects with respect to the GTED.

Figure 2: Follow-up of Randomized Subjects With Respect to the GTED

Collection of Study Endpoints and Safety Measures

Events in the CV composite endpoint: Investigators will be counseled to report any event that they assess as potentially to be a component of the study CV composite endpoint (refer to Section 9.2, Reporting/Adjudication of Events in the CV Composite Endpoint and Other Events for Adjudication).

Collection of Information After Early Withdrawal: Early withdrawal (for subjects prematurely discontinued)/end-of-treatment (for subjects completing the study) evaluation will be performed at the time the subject discontinues double-blind study drug or when the study ends (refer to Sections 9.1.4, End-of-Treatment/Early Withdrawal, and 9.1.5, Posttreatment Phase [Follow-Up] for collection of information on CV events and other assessments). In subjects that prematurely discontinue study drug, events in the CV composite endpoint, all deaths, serious adverse events and adverse events of fractures should continue to be collected until study completion.

Safety Evaluations and Adverse Events Requiring Collection of Additional Information: See Section 3.2, Safety Evaluations, for details around safety assessments and adverse events requiring collection of additional information. Investigators may also be asked to provide additional information on other adverse events, based upon review by the Medical Safety Review Committee (MSRC) or the study IDMC (refer to Sections 9.3.3, Medical Safety Review Committee, and 9.3.4, Independent Data Monitoring Committee).

Pharmacogenomic Blood Sample: A pharmacogenomic blood sample should be collected on Day 1 (or at a subsequent visit if not collected on Day 1) from subjects who consent separately to the pharmacogenomic component of the study to allow for pharmacogenomic research, as necessary (where local regulations permit). Subject participation in pharmacogenomic research is optional. Refusal to consent for this component does not exclude a subject from participation in the clinical study.

Substudies – Add-on Use with Specific AHAs

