9.1.4. End-of-Treatment/Early Withdrawal

The end-of-treatment/early withdrawal evaluation will be performed when the double-blind treatment phase of the study is ended or at the time the subject is withdrawn from the study. The evaluation should be performed as soon as possible after stopping the study drug.

Refer to the Time and Events Schedule that follows the Synopsis for procedures at the End-of-Treatment/Early Withdrawal evaluation.

Subjects who prematurely discontinue double-blind treatment will have follow-up contact as described in Section 9.1.5, Posttreatment Phase (Follow-Up) and in the Posttreatment Time and Events Schedule. If it becomes no longer possible for a subject to continue to make site visits for posttreatment measurement of vital signs and laboratory specimen collection, the investigator may revert to telephone contacts (with the subject or, as a last resort, with relatives or a family physician) or other available medical records to assess and collect information regarding serious adverse events, CV events, and fractures on the timelines described in the Time and Events Schedule, and forego the clinic visits. Alternately, at the investigator's discretion, less frequent in-clinic visits may be interspersed with other forms of contact, including telephone, email, letters, social media sources, fax, or other electronic or non-electronic means.

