9.1.5. Posttreatment Phase (Follow-Up)

All subjects should have a follow-up telephone contact (or optional study visit, at the discretion of the investigator) (if a telephone contact or study visit is not possible, follow-up information may be collected via email or other electronic or non-electronic means) approximately 30 days (but no more than 42 days) after the last dose of study drug to collect:

- Nonfatal CV events in the primary composite endpoint (nonfatal MI, nonfatal stroke)
- Death from any cause
- Nonfatal serious adverse events
- Adverse events of fracture

Subjects who discontinue treatment early for any reason (other than withdrawal of consent for follow-up contacts) will be contacted according to the Posttreatment Time and Events Schedule (or more frequently if necessary based on the investigator's knowledge of the subject) until completion of the overall study, with the goal of collecting any CV outcome events (ie, nonfatal events in the CV composite endpoint), deaths from any cause, adverse events of fracture, and any serious adverse events. Subjects who discontinue treatment less than 26 weeks before the completion of the study will be contacted by telephone at the end of the study to collect any of the events in the list above.

9.2. Reporting/Adjudication of Events in the CV Composite Endpoint and Other Events for Adjudication

Investigators will be counseled to report any event that they assess as potentially being a component of the study CV composite endpoints: CV death, nonfatal MI, and nonfatal stroke. In addition, all deaths (to determine cause of death) as well as events of hospitalized heart failure, will be submitted for adjudication.

For events of hospitalized unstable angina, adjudication will conclude with implementation of amendment INT-6. However, investigators will continue to report such events that are serious or that lead to study drug discontinuation on the eCRF.

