11.4. Safety Analyses

The safety analysis will be based on the mITT analysis set. The mITT analysis set includes all subjects who are randomly assigned to a treatment group and have received at least one dose of study drug and their data occurring between first dose and last dose plus 30 days. There will be no imputation for missing values for clinical laboratory test results or vital sign measurements in the analyses.

Safety and tolerability will be evaluated by summarizing and comparing the incidence of serious adverse events and adverse events of interest, discontinuation rate due to adverse events, clinically important changes in clinical laboratory tests, vital signs (pulse, blood pressure), and body weight between randomized groups. There will be no imputation for missing values for clinical laboratory test results or vital sign measurements in the analyses.

Adverse Events

The verbatim terms used in the eCRFs by investigators to identify adverse events will be coded using the Medical Dictionary for Regulatory Activities (MedDRA). All reported serious adverse events, adverse events resulting in study drug discontinuation, and adverse events of interest with onset during the treatment phase (ie, treatment-emergent adverse events) will be included in the analysis. For each adverse event, the percentage of subjects who experienced at least one occurrence of the given event will be summarized by treatment group. An adverse event will be considered to be a treatment-emergent

event if it occurs within 30 days of the last date of blinded study medication. The percentage of subjects with specific treatment-emergent adverse events will be summarized by severity and relationship to study drug, as classified by the investigators, for each treatment group.

Summaries, listings, datasets, or subject narratives may be provided, as appropriate, for those subjects who die, who discontinue treatment due to an adverse event, who experience a serious adverse event, or who experience an adverse event of interest.

Further analyses, described in the SAP for this study, will be conducted on the prespecified adverse events for which additional information is collected from the investigators (refer to Section 9.4, Safety Evaluations).

Clinical Laboratory Tests

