11.5. CV Outcomes and Efficacy Analyses

11.5.1. CV Outcomes (Primary Efficacy Endpoint)

The primary endpoint for CV benefit will be time to MACE, which is calculated as the time from randomization to the first occurrence of MACE. The statistical hypothesis will be:

$H_{0(1.0)}$: the HR = 1.0, versus $H_{1(1.0)}$: the HR \neq 1.0.

The primary analysis will be based on the ITT analysis set and the MACE events determined by the EAC to meet prespecified criteria. The primary comparison of canagliflozin to placebo will be based on the HR estimate derived from Cox proportional hazards model with terms for treatment, history of a previous CV event as fixed effects.

The assumption of the proportional HR will be examined. In case the assumption is deemed not reasonable, sensitivity analyses that do not rely on the constant HR assumption will be conducted to verify the results of the primary analysis.

Additionally, the HR and its 2-sided 95% CIs versus placebo will be assessed for each dose of canagliflozin. For individual components of the composite CV endpoint, the HR

and its 2-sided 95% CIs of canagliflozin combined doses relative to placebo will also be assessed.

Sensitivity analyses including CV endpoint events that occur within 30 days of the last dose of blinded study medication will be done.

The effects of different baseline demographic variables (eg, age, race, sex) as well as other important baseline disease characteristics (eg, history of prior CV disease, key concomitant therapy use, and region) on the primary endpoint will be explored; a detailed discussion of subgroup analyses will be provided in a SAP for this study, which will be finalized before the first interim analysis.

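### Section 11.4 ties the comparative safety analysis to last dose plus 30 days although serious events, deaths and fractures are collected off drug to study end, and the off-drug lists do not match Table 1 on non-serious events

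*Protocol*

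**What the plan says.** **Analysis.** Section 11.4 bases the safety analysis on the mITT set: randomised subjects with "at least one dose of study drug and their data occurring between first dose and last dose plus 30 days". Adverse events enter only if they are treatment-emergent, and an adverse event is a treatment-emergent "event if it occurs within 30 days of the last date of blinded study medication". The section also says that "Further analyses, described in the SAP for this study, will be conducted on the prespecified adverse events" for which additional information is collected, but gives no set or window for those analyses. It permits, without requiring, summaries, listings, datasets or narratives for subjects who die, have a serious event or have an event of interest.

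For the cardiovascular endpoint, Section 11.5.1 does the reverse: "The primary analysis will be based on the ITT analysis set and the MACE events determined by the EAC to meet prespecified criteria", and the 30-day version is a sensitivity analysis.

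**Off-drug collection.** For subjects who stop drug early, Section 3.1 says that, besides events in the CV composite, "all deaths, serious adverse events and adverse events of fractures should continue to be collected until study completion". Section 9.1.4 lets sites use telephone contacts or records to "assess and collect information regarding serious adverse events, CV events, and fractures on the timelines described in the Time and Events Schedule". Section 9.1.5 adds "deaths from any cause, adverse events of fracture, and any serious adverse events" to the CV outcome events. The Posttreatment Time and Events Schedule has a review row for "Serious adverse events and adverse events of fracture".

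**General collection.** Table 1 in Section 9.4 asks for every case, serious or not, of malignancy, photosensitivity, venous thromboembolism, fracture, male genital infection, amputation and diabetic ketoacidosis, and any pregnancy. Section 9.4 has events reported throughout the study from consent. Section 12.2.1 places events of interest on the eCRF. Section 9.4 and footnote u of the Time and Events Schedule require amputations to reach the sponsor within 24 hours of awareness. None of these texts has an on-drug limit.

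**The concern.** An on-treatment window is a normal choice for safety tables. The weakness is that it is the only comparative safety analysis the protocol states, while subjects are followed off drug partly to gather safety events.

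Two of the events concerned are live issues in this trial. Amputation is the main reason for Amendment INT-8, after the IDMC observed rates of 0.73, 0.54 and 0.30 per 100 patient-years on 100 mg, 300 mg and placebo (Section 1.1.2). The same section reports a fracture imbalance in this study. An on-treatment analysis alone cannot show whether either result holds over all follow-up.

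For amputation the limit is also tied to the outcome, because the conditions associated with amputation are themselves a reason to interrupt drug.

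The collection texts raise a second problem. A site reading Table 1 and a site reading the posttreatment schedule could record the same non-serious off-drug event differently. Any analysis of all follow-up would inherit that difference.

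**Working it through.** The plan gives no figure on this point to reproduce. The check sets the passages side by side, then adds one illustration.

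**1. Which off-drug events have a stated comparative analysis?**
- MACE: yes, on the ITT set (Section 11.5.1), with hazard ratios for the components in the same section. CV death is covered there.
- Non-CV deaths, other serious events and fractures more than 30 days after the last dose: collected (Sections 3.1, 9.1.4, 9.1.5 and the posttreatment schedule), but outside the mITT data and not treatment-emergent. Only the optional summaries or listings, or whatever the SAP adds, could use them.
- Section 11.1 leaves the alignment of ITT and mITT to the SAP for secondary endpoints. It does not say this for safety.

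**2. How the window acts on amputation.** Section 6.1 interrupts drug for lower-extremity infection, ulcer, osteomyelitis, gangrene or critical limb ischaemia until resolution. Sections 6.1 and 10.3 do not allow a restart after more than 90 days off drug. After an amputation, Section 6.1 makes restarting a matter for individual consideration and discussion with the sponsor. Read literally:
- Amputation within 30 days of the last dose taken: counted.
- Amputation later in an interruption, with drug then resumed: counted, because it falls between first and last dose.
- The same amputation, with drug not resumed: not counted.
- Amputation after more than 90 days off: not counted, because drug cannot be resumed.

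So whether an amputation is counted can depend on a restart decision that the amputation itself affects.

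**3. Non-serious events after drug is stopped.** The four off-drug lists name fracture as the only non-serious event. Table 1's collect-all column also holds amputation, malignancy, venous thromboembolism, photosensitivity, male genital infection and ketoacidosis, and any pregnancy. Serious cases are in both sets of texts, so the mismatch is confined to non-serious cases and pregnancy.

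**4. Illustration of follow-up outside the window.** The protocol gives no drug-stopping rate. The 5% annual dropout in Section 11.3 is a planning figure and is not defined as drug stopping. Assume a constant stopping rate r per year, no deaths, no restarts and follow-up T for everyone. With h = −ln(1 − r) and L = T − 30/365.25, the share outside is [L − (1 − exp(−hL))/h]/T.
- T = 4.5 years (mean follow-up in Section 1.1.2), r = 5%: h = 0.0513, L = 4.418, (4.418 − 3.953)/4.5 = 10.3%. For r = 3% and 10%: 6.3% and 19.7%.
- T = 7.25 years (maximum in Section 3.1), r = 5%: L = 7.168, (7.168 − 5.998)/7.25 = 16.1%. For r = 3% and 10%: 10.0% and 29.5%.

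These shares describe person-time under assumed rates. If events and time are lost in equal proportion in every arm, the rate ratio is unchanged and only precision falls. The illustration is therefore no evidence of bias.

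**The case against.** The strongest reply is that much of this belongs to the SAP. Section 11 calls itself a general description, and Section 11.4 leaves further analyses of prespecified events to the SAP with a reference to Section 9.4, where amputation, fracture and malignancy are listed. That stands as far as it goes: a reader might infer that no analysis of all follow-up is planned, and the documents do not support that. What remains is that Section 11.4 is not silent. It fixes one window for the comparative analysis and names no other.

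A reader might also infer that off-drug safety data go unused. That is too strong. The optional summaries and listings carry no treatment-emergent limit, and Section 9.3.4 has the IDMC review accumulated unblinded safety data. Neither, however, is a stated between-group analysis of off-drug events in the study report.

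On collection, a reader might infer that off-drug amputations are missed. They should not be. Serious ones are collected, the 24-hour rule covers every amputation, Section 12.2.1 keeps all adverse events in source documents, and the posttreatment schedule adds foot examinations and questions about foot problems. The definition of seriousness in Section 12.1.1 is broad, so many amputations and malignancies would qualify. The off-drug lists do not say they are exhaustive, and Section 9.4 points to Sections 9.1.4 and 9.1.5 for posttreatment collection, so one could argue that the narrower list governs. But nothing says that Table 1 ends when drug is stopped. The question of what goes on the eCRF is open.

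**Conclusion.** The point holds as a cheap improvement. Section 11.4 states only an on-treatment comparative safety analysis, although the protocol collects serious events, deaths and fractures off drug to study completion. For amputation, exclusion from the window is linked to the outcome through the interruption rule.

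It may be tempting to say that the amputation comparison will be biased, or biased toward no harm. The documents do not support that: they give no count of amputations more than 30 days after the last dose and no stopping rates by arm, so neither direction nor size can be derived. The 6% to 30% of follow-up in the illustration rests wholly on assumed stopping rates.

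The collection conflict holds independently of the SAP. It is limited to whether the non-serious events in Table 1's collect-all column, and pregnancy, go on the eCRF after drug is stopped.

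**What to change.** 1. In Section 11.4, keep mITT for the general adverse event tables. For amputation, fracture and malignancy, add an analysis of all follow-up from randomisation to last contact regardless of drug, with rates per 100 subject-years and a hazard ratio with 95% CI, shown beside the on-treatment analysis.
2. Reconcile Section 3.1, Section 9.1.4, Section 9.1.5 and the posttreatment schedule with Table 1, Section 9.4, Section 12.2.1 and the 24-hour amputation rule. State whether non-serious amputation, malignancy, venous thromboembolism, photosensitivity, male genital infection and ketoacidosis, and any pregnancy, are recorded on the eCRF after drug is stopped. If they are not, label the off-drug part of the amputation and malignancy analyses as serious cases only.

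The cost is one paragraph, a few tables from data mostly already collected, and one wording alignment; the posttreatment contacts already take place. The downside is that off-drug time may dilute an acute effect (Section 1.1.2 places the fracture imbalance initially within the first 26 weeks), which is why both analyses should be shown. No change to any drug-interruption rule is implied.

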During a routine review of unblinded interim data from the ongoing CANVAS study, the Independent Data Monitoring Committee observed a non-dose-dependent increase in the incidence of non-traumatic, lower-extremity amputations (mostly of the toes) in the canagliflozin 100 mg and 300 mg groups compared to placebo. With a mean duration of follow-up in CANVAS of approximately 4.5 years, the annualized incidence of lower-extremity amputation was 0.73, 0.54, and 0.30 events per 100 patient-years in the canagliflozin 100 mg, canagliflozin 300 mg, and placebo groups, respectively. Overall, treatment with canagliflozin was associated with an approximately 2-fold increase in amputation event rates (relative risk [RR] 2.15; 95% CI: 1.3- 3.5). The CANVAS/CANVAS-R IDMC, which has access to unblinded CV outcomes data, notified the sponsor that “after consideration of all outcomes, the IDMC feels the study should continue.” Infections were the events most commonly associated with amputations, and most amputations were of the toe. The factors associated with the greatest risk for amputation included prior amputation, peripheral vascular disease, and neuropathy.

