Subjects will remain on a stable regimen (medications and doses) of their current AHA regimen through Week 18 of the double-blind treatment phase, unless down-titration is required to manage or avoid hypoglycemia, or unless glycemic rescue criteria are met (refer to Section 6.2.2, Glycemic Rescue Therapy Through Week 18: Criteria and Implementation). After the AHA regimen stable period is completed at Week 18, the investigator should adjust the subject's AHA regimen so as to achieve target glycemic control, per standard diabetes care guidances, individualized as considered appropriate by the investigator. *Adjustments in the AHA regimen should be carefully implemented throughout the study to avoid events of hypoglycemia.*

Planned Meta-analyses (CANVAS and Other Canagliflozin Studies)

[figure not shown]
As described in Section 11.8, Meta-analyses to Support Regulatory Requirements, during the conduct of this study, data from CANVAS will be exported and integrated with data from other large, well-controlled, double-blind, randomized studies of canagliflozin to support meta-analysis to assess the rate of important CV events in a prespecified composite endpoint.

Study Duration

Subjects are expected to be followed for a maximum of approximately 7.25 years with the last visit for the last subject targeted to occur when at least 688 MACE events are accumulated between the CANVAS and CANVAS-R studies. All sites will be notified of the projected global trial end date (GTED) which is projected to occur prior to April 2017. The GTED is the stopping date of the study (ie, targeted date when the last subject completes last study visit), which will be announced to investigators at a time point when the actual accrual of events approaches the number of events required for the analysis; the announcement of the GTED may occur approximately 3 months prior to the GTED. Immediately after the projected GTED notification is sent, for subjects who remain on double-blind study drug, sites will be required to schedule the last on treatment visits and the 30-day off drug follow-up visits as per the Time and Events Schedule; for subjects who prematurely discontinue study drug, sites will be required to make a final contact (eg, schedule the last follow-up visit) or vital status check as soon as possible after announcement of GTED.

All visits (including the 30-day off drug follow-up visit) will need to be completed prior to the GTED.

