11.3. Sample Size Determination

The sample size for the recruitment of the initial 4,500 subjects was based upon having a sufficient number of participants to support, in concert with the other controlled clinical trials in the canagliflozin development program, a detailed pre-approval assessment of the safety and tolerability of canagliflozin. Data from this initial cohort were exported and integrated with data from other Phase 3 well-controlled studies to support a planned pre-approval meta-analysis to demonstrate that the upper bound of the 2-sided 95% CI for the CV HR of canagliflozin relative to control in composite endpoint events (MACE and hospitalized unstable angina) was <1.8 ; the current US regulatory requirements for filing. The FDA post-marketing requirements for canagliflozin demand a subsequent estimate of CV safety that will be performed on data from CANVAS and CANVAS-R, when sufficient events have occurred to demonstrate that the upper bound of the 95% CI HR is <1.3 based on MACE (excluding hospitalized unstable angina).

The assumed per annum event rate is 2.25% and the per annum dropout rate is 5%. With an enrollment period 1.5 years, 4,500 randomized subjects were projected to contribute sufficient CV events to support the pre-approval CV meta-analysis.

The original phased recruitment strategy allowed for an interim assessment of study feasibility to demonstrate the primary hypothesis of CV benefit using the results of the interim analysis. Results from the interim analysis (conducted after approximately 2 to

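### Section 11.4 compares adverse events as crude on-drug percentages, which shift if the arms stop drug at different rates; exposure-based and all-follow-up estimates should be added

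*Protocol*

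**What the plan says.** Section 11.4 (Safety Analyses) uses the mITT set, meaning treated subjects and "their data occurring between first dose and last dose plus 30 days". It states the comparison directly: "Safety and tolerability will be evaluated by summarizing and comparing the incidence of serious adverse events and adverse events of interest", between randomized groups. Per event type, it says that "the percentage of subjects who experienced at least one occurrence of the given event will be summarized by treatment group". Anything reported counts as a treatment-emergent "event if it occurs within 30 days of the last date of blinded study medication". Person-time, time to event and exposure adjustment are not mentioned. For adverse events with additional data collection, the section refers to further analyses in the SAP without describing them.

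Section 3.1 sets the horizon: "Subjects are expected to be followed for a maximum of approximately 7.25 years". Section 11.3 gives a 1.5-year enrollment period and one annual dropout figure, 5%, for all arms.

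Where the protocol reports its own safety results (Section 1.1.2), it uses person-time. For amputation, "the annualized incidence of lower-extremity amputation was 0.73, 0.54, and 0.30 events per 100 patient-years" in the 100 mg, 300 mg and placebo groups. Fractures and DKA-related serious adverse events are also given per 100 subject-years.

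Sections 3.1 and 9.1.5 and the posttreatment schedule require serious adverse events and fractures to be collected after drug is stopped, until the study ends. Section 11.4 describes no analysis of those off-drug data.

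**The concern.** Safety and tolerability is one of the two primary objectives (Section 2.1.1). Within an on-drug window, the chance of recording at least one event rises with time on drug. Randomization and a common end date balance calendar follow-up, so the wide spread in individual exposure does no harm in itself. Only a difference between arms in stopping drug matters. If canagliflozin is stopped more often, its percentages fall and a real excess is diluted. If placebo is stopped more often, the ratio is inflated.

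The protocol gives reasons why stopping might differ:
- Program-wide, discontinuation for adverse events was slightly higher than in controls, though generally low (Section 1.1.2).
- A serious adverse event of biochemically confirmed DKA requires withdrawal from drug (Section 10.2).
- Drug is interrupted for conditions associated with amputation (Section 6.1), and subjects off drug for more than 90 days should not restart (Section 10.3).

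Stopping can therefore be related to the harms being counted.

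**Working it through.** **1. The protocol's own ratio.** Amputation, both doses weighted equally: ((0.73 + 0.54)/2)/0.30 = 0.635/0.30 = 2.12, against the stated 2.15. Rounding of the three rates allows about 2.07 to 2.17, so the stated figure is consistent with a ratio of person-time rates.

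**2. Crude percentage under unequal stopping.** Inputs from the protocol: placebo fracture rate λ = 0.011 per year (Section 1.1.2); window lag L = 30/365.25 = 0.082 years (Section 11.4); follow-up F uniform from 5.75 to 7.25 years (7.25 years less up to 1.5 years of enrollment); N = 4,330, allocated 2:1 for combined doses versus placebo. Assumed: the annual discontinuation probability p in each arm, constant hazards, and stopping independent of the event.

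With d = −ln(1 − p) and A = F − L:
- mean window W = L + (1 − e^(−dA))/d
- P(at least one event) = 1 − [ d/(d+λ) · e^(−λL) · (1 − e^(−(d+λ)A)) + e^(−dA) · e^(−λF) ]

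Both are averaged over F. Example at the midpoint F = 6.5 (A = 6.418):
- p = 5%: d = 0.0513, W = 0.082 + (1 − 0.7195)/0.0513 = 5.55 years
- p = 10%: d = 0.1054, W = 0.082 + (1 − 0.5085)/0.1054 = 4.75 years (4.74 averaged over F)

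No true effect, λ = 0.011:

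| Annual stopping, placebo vs canagliflozin | Crude %, placebo vs canagliflozin | Crude RR | Ratio of mean windows |
|---|---|---|---|
| 5% vs 5% | 5.90 vs 5.90 | 1.00 | 1.00 |
| 5% vs 7% | 5.90 vs 5.54 | 0.94 | 0.94 |
| 7% vs 5% | 5.54 vs 5.90 | 1.06 | 1.06 |
| 5% vs 10% | 5.90 vs 5.05 | 0.86 | 0.86 |
| 10% vs 5% | 5.05 vs 5.90 | 1.17 | 1.17 |

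A 4-point gap, taking 6% and 10% as yearly hazards with F fixed at 6.5 years, gives a crude RR of 0.89 one way and 1.12 the other. Under these assumptions the ratio of events per subject-year is 1.00 in every row.

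At 5% vs 10%, the probability of a nominally significant (2-sided 0.05) difference with no true effect is about 9% for events at 0.3 per 100 subject-years, 22% at 1.1, 35% at 2 and 69% at 5.

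**3. With a true effect.**

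| True HR (placebo rate per 100 subject-years) | 5% vs 5% | 5% vs 7% | 5% vs 10% |
|---|---|---|---|
| 1.45 = 1.6/1.1, fractures (1.1) | RR 1.43, power 86% | RR 1.35, power 69% | RR 1.23, power 38% |
| 2.15, amputation (0.3) | RR 2.13, power 95% | RR 2.00, power 90% | RR 1.82, power 78% |

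**4. The mechanism in the protocol's own data.** DKA-related serious adverse events, program-wide (Section 1.1.2):
- By percentage: (10/10,687)/(2/6,909) = 0.0936%/0.0289% = 3.23.
- Implied subject-years: 4/0.000522 + 6/0.000763 = 7,663 + 7,864 = 15,527 on canagliflozin; 2/0.000238 = 8,403 on comparator.
- By rate: (10/15,527)/(2/8,403) = 0.0644/0.0238 per 100 subject-years = 2.71.

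The gap is the exposure ratio: 15,527/10,687 = 1.45 years against 8,403/6,909 = 1.22 years, a factor of 1.19 = 3.23/2.71. These data mix studies of different length, so they illustrate the mechanism and do not estimate a bias in CANVAS.

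**The case against.** The strongest reply is that this belongs to the SAP. Section 11 calls itself a general description, and Section 11.4 promises further SAP analyses for adverse events with additional data collection, which plausibly include fracture, amputation and DKA. Nothing in Section 11.4 excludes rates, and the program already reports these harms per subject-year. This stands in part. A reader might infer that no exposure-adjusted safety analysis will be done, and the documents do not support that. What remains is that the only adverse-event measure Section 11.4 names is the crude percentage, and that the deferral neither promises exposure adjustment nor covers the remaining serious and discontinuation-related events.

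Second, the size is assumed. A reader might infer that a harm signal will be created or hidden in this trial. The documents do not show that: they give no stopping rates by arm, and the only directional statement is program-wide and describes a slight difference. Even at 5% vs 10%, an amputation effect of 2.15 would still appear as about 1.8.

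Third, a reader might take person-time rates as a full cure. The ratio of 1.00 in every row follows from constant hazards and independent stopping. The protocol undercuts both: the fracture imbalance initially arose within the first 26 weeks (Section 1.1.2), and stopping may be informative. On-drug rates and hazard ratios keep the second problem.

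**Conclusion.** The point holds as a limited one. The crude on-drug percentage named in Section 11.4 is distorted roughly in proportion to the ratio of mean on-drug time between arms. With no true effect, the crude RR moves by about 6% for a 2-point annual gap in stopping. For a 4- to 5-point gap it falls by about 11 to 14% if canagliflozin is stopped more, or rises by 12 to 17% if placebo is. With equal stopping the distortion is essentially zero. These figures rest on assumed discontinuation rates, constant hazards and independent stopping; the actual size cannot be read from the protocol. Modest effects on commoner events are the most exposed, and a doubling of amputation the least. This is a worthwhile improvement to the stated measure, not evidence that the trial's safety conclusions will be wrong.

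**What to change.** In Section 11.4, for serious adverse events, adverse events leading to discontinuation and adverse events of interest:

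- Add incidence per 100 subject-years at risk and a time-to-first-event hazard ratio with 95% CI, canagliflozin versus placebo. Keep the percentages as descriptive.
- For serious adverse events and fractures, add a time-to-first-event analysis over all follow-up, on or off drug, with cumulative-incidence curves. This addresses informative stopping and shows a hazard that is not constant.
- If the SAP already contains these analyses, a sentence in Section 11.4 pointing to them is enough.

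No new data are needed, since the off-drug events are already collected. The cost is extra safety-table columns and modest programming.
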